3.4 Records

Each subject will be assigned a number. The numbers will be consecutive starting at 001.

A record will be created for each subject. Each record will contain a medical history, and the subject's efficacy parameters copied from the subject's charts and documented in the appropriate CRF.

The subjects' records will be stored and handled in the same manner as the PI's other clinical study patients' records are stored i.e., in a locked research storage area.

No other data will be recorded. No personal information will be kept outside the study site.

Data compiled at the end of the study will not include any information that can be used to identify individuals.

3.5 Duration

The duration of the study is 28 days. There will be no study related follow-up treatment.

3.6 Discontinuation

In the event that a subject experiences a SAE or an AE grade 3 or 4 (defined in Section 6) we will discontinue the study for that particular subject.

In the event a subject in any arm experiences a SAE defined as death not due to respiratory failure (presents with clear lung CT and no ARDS symptoms) the study will be discontinued. The remainder of the study shall continue.

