3.1 Primary Study Endpoints/Secondary Endpoints

Primary Outcome Measure:

1. Treatment efficacy of Proxalutamide relative to placebo arm as assessed by the COVID-19 ordinal scale (defined in Section 5.1) [Time Frame: Day 14]

Secondary Outcome Measures:

1. Treatment efficacy of Proxalutamide relative to placebo arm as assessed by the COVID-19 ordinal scale (defined in Section 5.1) [Time Frame: Day 28]
2. Time to recovery [Time Frame: Day 1 through Day 28]
Recovery is defined as the first day on which the subject satisfies one of the following two categories from the ordinal scale (defined in Section 5.1): 2) Not hospitalized, limitation on activities and/or requiring home oxygen; 1) Not hospitalized, no limitations on activities.
3. Proportion of death [Time Frame: Day 1 through Day 28]
Defined as the number of subjects who have died in each arm divided by the numbers of subjects randomized to the treatment arm
4. Duration of new oxygen use [Time Frame: Day 1 through Day 28]
Duration of new oxygen use measured in days among subjects that did not require oxygen upon randomization.
5. Proportion of subjects testing positive for SARS-CoV-2 [Time Frame: Day 14]
Defined as the proportion of subjects in each arm with a qualitative positive rtPCR SARS-CoV-2 test from upper respiratory tract specimens

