3.2 Study Design/Type

This study is designed as a prospective, interventional, placebo controlled, double-blinded, randomized parallel assignment study. The study will have 2 cohorts: men and women and 2 arms:

Arm 1: Subjects administered Proxalutamide 300mg q.d for 14 days + standard of care as determined by the PI at the site

Arm 2: Subjects administered Proxalutamide placebo 300mg q.d for 14 days + standard of care as determined by the PI at the site

Study Environment:

This is a multi-center study to be conducted at multiple hospitals (the sites). This exact protocol will be followed during the study. There will be one or more PIs. The study will be approved by the appropriate Ethics Committees (IRBs). Data collection will be performed at each site by study personnel under the supervision of the PI.

Study Design:

Phase I: Enrollment (within 5 days of admission to hospital):

1. Each subject will be evaluated for the inclusion and exclusion criteria

2. Each subject will undergo a physical examination
3. Each subject (or legally authorized representative) will complete and sign the Informed Consent Form
4. Each subject will be assigned a subject study number
5. Each subject will be randomly assigned to an Arm (Section 3.3)
6. Based on the Arm assignment, each subject will be administered the intervention
7. All information will be recorded in the appropriate CRFs

Phase II: Outcome Assessment at Site (days 1-28):

1. Each subject will be evaluated daily by the PI for the outcomes of this study
2. Based on the Arm assignment, each subject will be administered the intervention
3. The PI will assess each subject for any treatment related adverse events
4. All information will be recorded in the appropriate CRFs

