5.1 Efficacy Parameters

The following efficacy parameters will be assessed and recorded in the CRF.

I. COVID-19 Ordinal Scale:

The ordinal scale is an assessment of the clinical status of each subject. The scale is defined as follows:

- 8. Death;
- 7. Hospitalized, on invasive mechanical ventilation or ECMO;
- 6. Hospitalized, on non-invasive ventilation or high flow oxygen devices;
- 5. Hospitalized, requiring supplemental oxygen;

4. Hospitalized, not requiring supplemental oxygen- requiring ongoing medical care (COVID-19 related or otherwise);
3. Hospitalized, not requiring supplemental oxygen - no longer requires ongoing medical care;
2. Not hospitalized, limitation on activities;
1. Not hospitalized, no limitations on activities

II. Time to Recovery:

Time to recovery is defined as the first day on which the subject satisfies one of the following three categories from the ordinal scale (defined in Section 5.1): 3)

Hospitalized, not requiring supplemental oxygen - no longer requires ongoing medical care; 2) Not hospitalized, limitation on activities and/or requiring home oxygen; or 1) Not hospitalized, no limitations on activities.

III. “Multiple Combined Sensitive Outcome Detect Method” (combining items I and II):

1. (WHO COVID ORDINAL OUTCOMES SCALE):
 - a. 1 dia; b. 2 dias; c. 3 dias; d. 7 dias; e. 14 dias; f. 21 dias; g. 30 dias (cuja escala é plenamente contemplada por alguns dos desfechos descritos abaixo)
2. TEMPO ATÉ RECUPERAÇÃO – regressão aos níveis 1 e 2 da WHO COVID Ordinal Outcomes Scale (dias)
3. POSITIVIDADE DA rtPCR-SARS-CoV-2 a. 7 dias; b. 14 dias; c. 30 dias (%)
4. TEMPO ATÉ REMISSÃO DE CADA SINTOMA (dias)
5. TEMPO ATÉ REMISSÃO COMPLETA DOS SINTOMAS (dias)
6. TEMPO ATÉ RECUPERAÇÃO DA CAPACIDADE DE REALIZAÇÃO DE ATIVIDADES DIÁRIAS DEVIDO AOS SINTOMAS DE COVID-19 (Nível 1 da WHO COVID Ordinal Outcomes Scale) (dias)

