13. NECESSIDADE DE USO DE VASOATIVOS (%)
14. MORTE (%)

5.2 Method and Timing

For each study day while the subject is hospitalized, the PI will record the clinical assessment on an 8- point ordinal scale as follows:

- Day 1 – The clinical assessment at the time of enrollment.

- Day 2 - The most severe clinical assessment occurring any time between enrollment and midnight the day following enrollment.
- Day 3-28 (or until discharged) - The most severe assessment occurring from midnight to midnight of the prior day (e.g., the value recorded on Day 3 will be the most severe outcome that occurred on Day 2).

If the subject is no longer hospitalized at day 28, a clinical assessment will be made by an in-person or phone visit; otherwise, it would be recorded as missing data.

6 Assessment of Safety

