6.3 Adverse Events

6.3.1 Definition of Adverse Event (AE)

AE means any medical event associated with the use of an intervention, whether or not considered intervention-related. An AE can be any unfavorable and unintended sign (including an abnormal laboratory finding), symptom, or disease temporally associated with the use of medicinal (investigational) product.

Any medical condition that is present at the time that the subject is screened will be considered as baseline and not reported as an AE. However, if the severity of any pre-existing medical condition increases, it should be recorded as an AE.

Given the nature of severity of the underlying illness, subjects will have many symptoms and abnormalities in vitals and laboratory. All Grade 3 and 4 AEs will be captured as AEs in this trial.

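### The Day-14 ordinal score is not secured after a Section 3.6 exit or an early discharge, and no rule covers missing scores

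*Combined protocol and SAP*

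**What the plan says.** The document prints two protocol versions. Section numbers below refer to the current (male and female) version unless stated.

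- **Exit.** Section 3.6: where a subject "experiences a SAE or an AE grade 3 or 4 (defined in Section 6) we will discontinue the study for that particular subject". It speaks of the study, not of the drug, and does not require the event to be drug-related.
- **What can trigger it.** Section 6.3.1 counts increased severity of a condition present at screening as an adverse event (AE), and remarks: "Given the nature of severity of the underlying illness, subjects will have many symptoms and abnormalities in vitals and laboratory". Section 6.3.2 includes prolonged hospital stay among serious adverse events (SAEs). The fallback grading in 6.3.5 puts events that materially change clinical status in Grade 3.
- **Continued observation.** Section 3.2, for days 1 to 28: "Each subject will be evaluated daily by the PI for the outcomes of this study". Section 5.1.III lists the ordinal scale at "a. 1 dia; b. 2 dias; c. 3 dias; d. 7 dias; e. 14 dias; f. 21 dias; g. 30 dias". Section 6.2 sets laboratory tests at Day 14 and daily AE assessment over 28 days. Sections 6.3.2 and 6.3.7 follow SAEs until they resolve or stabilise, and record SAEs and Grade 3-4 AEs to Day 28.
- **Scoring.** Section 5.2: "For each study day while the subject is hospitalized, the PI will record the clinical assessment". For a patient out of hospital at Day 28, the score comes from an "in-person or phone visit; otherwise, it would be recorded as missing data". No such contact is named at Day 14, the primary time point in 3.1 and 7.1.II. In the earlier male-only version, Section 5.2 placed this contact at Day 14.
- **Missing scores.** Section 7.1.III says missing data will be described, and section 5 of the final statistical plan says they were reported. Neither gives a rule for analysis.

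**The concern.** An exit under 3.6 is more likely in a patient who is doing badly, which is what the ordinal scale measures. If the score stops at that exit, Day-14 status is lost for reasons linked to outcome. If treatment changes the frequency of such events, the loss also differs by arm. Randomisation does not protect the recovery ratio against that, and the direction of the error is not known in advance.

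Two further gaps add to this. With no stated rule for missing status, the choice can be made with results in view; the final plan says that it was adjusted during manuscript writing. That plan also defines recovery as reaching scores 1 and 2, which leaves open how to count a patient discharged and then readmitted or dead by Day 14.

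**Working it through.** **1. The passages side by side.** Take a patient with a non-fatal Grade 3 worsening on Day 6 who is alive on Day 14. Under 3.6 read literally, the study has ended for him. Under 3.2 he is evaluated daily to Day 28. Under 5.2 he is scored on each day in hospital. Sections 6.2, 6.3.2 and 6.3.7 continue safety follow-up without naming the score. A site could cite the protocol for recording a Day-14 score or for not recording one. For a patient discharged on Day 9, 5.2 stops the daily score, and the next score contact it names is Day 28.

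**2. The plan's own figure.** Section 7.2 uses N = 12(z_a + z_b)^2 / [L^2 (1 - sum p^3)], where L is the log odds ratio. With 1.960, 1.2816 and ln 2, 12(3.2416)^2 / 0.4805 = 262.4. The category probabilities are not in the documents, so 294 can only be checked for consistency. 294 x 0.965 = 283.7 evaluable patients, which implies 1 - sum p^3 = 262.4/283.7 = 0.925. An odds ratio of 2.0 over 39% gives 56.1%, or 47.6% combined. N then runs from 281 (even spread within the recovered and not-recovered categories) to 364 (only two categories filled), so 294 is compatible with the inputs.

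**3. How far two ordinary rules differ.** Let R be true recovery in an arm, L now the share lost, and q recovery among the lost, with subscripts a (active) and p (placebo).

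- Lost excluded: [(Ra - qa La)/(1 - La)] / [(Rp - qp Lp)/(1 - Lp)]
- Lost counted as not recovered: (Ra - qa La) / (Rp - qp Lp)
- Second divided by first: (1 - La)/(1 - Lp), whatever R and q are

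The only loss figure in the documents is 3.5% (Section 7.2): 0.035 x 294 = 10.29 patients, and 10.29/147 = 7.0% if all are in one arm.

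| Loss, active vs placebo | Source | Factor |
|---|---|---|
| 0% vs 7% | plan's 3.5%, extreme split | 1/0.93 = 1.075 |
| 7% vs 0% | plan's 3.5%, extreme split | 0.93 |
| 10% vs 20% | assumed | 0.90/0.80 = 1.125 |
| 15% vs 30% | assumed | 0.85/0.70 = 1.21 |
| equal | - | 1.00 |

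Reversing the assumed rows gives 0.89 and 0.82. These factors apply to a planned ratio of 1.36.

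**4. Bias with no true effect.** Set R = 0.39 in both arms and assume 10% active versus 20% placebo lost. Counting the lost as recovered uses (R - q La + La)/(R - q Lp + Lp). The true ratio is 1.00.

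| q | Excluded | Not recovered | Recovered |
|---|---|---|---|
| 0% | 0.89 | 0.39/0.39 = 1.00 | 0.49/0.59 = 0.83 |
| 20% | 0.94 | 0.37/0.35 = 1.06 | 0.47/0.55 = 0.85 |
| 39% | 1.00 | 0.351/0.312 = 1.13 | 0.451/0.512 = 0.88 |
| 60% | 1.09 | 0.33/0.27 = 1.22 | 0.43/0.47 = 0.91 |

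These are examples, not bounds.

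**5. The ordinal test.** The final plan still tests the distribution. A simulation with no true effect used 4,000 trials of 147 per arm, assumed Day-14 shares for scores 1 to 8 of 0.25, 0.14, 0.05, 0.13, 0.18, 0.08, 0.07 and 0.10, and loss only among scores 5 to 7. The complete-case Wilcoxon test rejected in 5.0% of trials with 9.9% lost per arm, 8.4% with 9.9% versus 3.3%, and 14.0% with 16.5% versus 6.6%.

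**6. Early discharge.** The expected share discharged near Day 14 is (0.39 + 0.53)/2 = 0.46 using the final plan's 14-point difference, or (0.39 + 0.561)/2 = 0.476 using the odds ratio. If scores 1 and 2 cannot be separated for these patients, sum p^3 rises by 3 x p1 x p2 x s, where s is that share. For s = 0.476 this is 0.081 (50:50 split) or 0.052 (80:20), and power falls from 90% to 87.2% or 88.3%. For s = 0.46 it is 87.5% or 88.5%.

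**7. Section 4.3.** Its 14 days of follow-up after investigator withdrawal have no stated start. Counted from withdrawal on Day w they end on Day w + 14; counted from enrolment, about Day 14. Both reach the primary time point. For w below 14, neither reaches Day 28. The section does not name the score or refer to 3.6.

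**The case against.** The strongest reply is that the plan presupposes observation to Day 28 almost everywhere else. Section 5.2 requires a daily score for inpatients with no exception for 3.6, and many patients with a severe event will still be inpatients. Section 6.2 plans Day-14 laboratory tests. Section 5.1.III lists a Day-14 score; its Day-30 entry in a 28-day study is a separate slip and does not cancel it. Section 3.6 uses the word study loosely, since its second paragraph discontinues the study and then lets the remainder continue. Section 7.3 analyses everyone enrolled, which largely answers where replaced subjects belong. No rate of 3.6 exits is given, so every loss figure above 3.5% is assumed.

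Most of this stands, and it limits the point to a conflict between sections. A reader might infer that Day-14 scores were in fact lost after severe events. The documents do not show that. Nor does the dropping of duration of new oxygen use, which the final plan attributes to inadequate site reporting: it is a different variable. A reader might also infer that early discharge endangers the recovery ratio itself. It mostly does not, because a live discharge implies score 1 or 2 unless readmission or death follows by Day 14.

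The reply does not supply a statement that the score continues after a 3.6 exit, a named Day-14 score contact after discharge, or a rule for a missing score.

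**Conclusion.** The point holds as a conflict between sections and a missing safeguard on the primary outcome, and it should be fixed. Section 3.6 followed literally can remove Day-14 status in patients who worsen, Section 5.2 does not schedule the score at Day 14 after discharge, and nothing says how a missing score is analysed.

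On the plan's own 3.5%, the choice between two ordinary rules moves the recovery ratio by at most about 7% either way, and only if all the loss falls in one arm. Larger shifts need larger, unequal losses, for which the documents give no figure. Equal loss makes the two rules agree. A reader might infer bias in favour of the active arm, but the sign depends on which arm loses more, on recovery among the lost and on the rule used. For early discharge, what is exposed is the split between scores 1 and 2 (about 2 to 3 points of power on the ordinal test) and events between discharge and Day 14. The power figures rest on a sum p^3 solved back from 294. Mortality at 28 days is less exposed, because 6.3.7 has SAEs, which include deaths, recorded to Day 28.

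**What to change.** **Protocol wording.** Reconcile 3.6 and 4.3 with 3.2, 6.2, 6.3.2 and 6.3.7. State that an AE, stopping treatment or investigator withdrawal does not end outcome follow-up, and that the ordinal score and vital status are collected to Day 28 for every randomised patient who has not withdrawn consent. In 5.2, restore the in-person or phone score at Day 14 alongside Day 28. No change to when treatment stops is proposed.

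**Analysis.** Define recovery by status at Day 14, so that a patient readmitted or dead by then is not recovered. A live discharge with no recorded readmission or death by Day 14 should not be treated as missing for the binary outcome. Analyse missing Day-14 status as not recovered. In the step 4 example this is closer to the truth than exclusion when few of the lost recover, and the two are about equally far off at 20%. Add two sensitivity analyses: complete case, and missing counted as recovered. Report missing and replaced patients by arm.

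**Cost.** The wording, plus one contact per patient discharged before Day 14: about 0.46 x 294 = 135 to 0.476 x 294 = 140 per cohort on the plan's assumptions. If data collection is complete, contacts can no longer be added. The cost is then the definition, one rule, two sensitivity analyses and one table, all labelled post hoc.

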3.7 Product Accountability

All interventional treatments for this study will be stored and monitored according to each hospital standard protocol.

3.8 Data Identification

The subject records kept by the PI will be stored and handled in the same manner as the PI's other clinical research subject records. Only authorized personnel named in this study, or medical professional retained by the PI in case of an adverse event, will have access to the subject records.

No other data will be recorded. No personal information will be kept outside the study site.

Data compiled at the end of the study will not include any information that can be used to identify individuals.

4. Selection and Withdrawal of Subjects

4.1 Inclusion Criteria

1. Admitted to the hospital with symptoms of COVID-19
2. Male and females age ≥ 18 years old
3. Laboratory confirmed positive SARS-CoV-2 rtPCR test within 7 days prior to randomization or confirmed lung involvement by CT scan
4. Clinical status on the COVID-19 Ordinal Scale (defined in Section 5.1) of 3 to 6
5. Coagulation: INR $\leq 1.5 \times \text{ULN}$, and APTT $\leq 1.5 \times \text{ULN}$
6. Subject (or legally authorized representative) gives written informed consent prior to performing any study procedures
7. Subject (or legally authorized representative) agree that subject will not participate in another COVID-19 trial while participating in this study

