3.3 Randomization

During the enrollment phase (admission to hospital), each subject will be assigned a subject study number. The first subject will be assigned the number 001 and each subject thereafter will be assigned a consecutive number i.e., 002, 003, etc.

In each cohort, subjects will be randomized into 1 of 2 arms in a 1:1 ratio each receiving an interventional treatment.

Arm 1: Subjects administered Proxalutamide 300mg q.d for 14 days + standard of care as determined by the PI at the site

Arm 2: Subjects administered Proxalutamide placebo 300mg q.d for 14 days + standard of care as determined by the PI at the site

In each cohort, each subject will be randomized using an interactive web software: Randomizer.at. The blinding table layout will be a single block. The randomization method used will be permuted blocks of size 4.

This is a blinded study. Neither participants, nor investigators, nor the study team will be aware of treatment assignments prior to the final data base locks at the conclusion of the study (or the interim analysis).

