6.4.3 Reporting Unanticipated Problems to Subjects

Subjects will be informed of any UPs that occur as part of their participation in this trial.

7 Statistical Plan

7.1 *Statistical Methods*

I. General Principles:

- Double-blinded, placebo controlled randomized interventional study with a two-sided type I error rate of 0.05.
- Continuous variables will be expressed as median (interquartile range [IQR]) and categorical variables will be expressed as a number
- 95% confidence intervals will be calculated for the primary outcome
- Group comparisons will be analyzed by the Wilcoxon rank sum test or χ^2 test
- The placebo arm will be used as a reference group when calculating treatment effects
- Differences between rates of clinical improvement will be calculated using unadjusted ordinal logistic regression or Cox proportional hazard models
- Statistical analyses will be conducted using XLSTAT version 2020.5.1 (Addinsoft, Inc.)

II. Statistical Hypotheses:

The primary endpoint is the distribution of clinical assessments on the COVID-19 ordinal scale at day 14. The primary outcome will be analyzed using the Wilcoxon rank sum test.

The Null Hypothesis (H_0) is that the distribution of clinical assessments on the COVID-19 ordinal scale at day 14 among hospitalized COVID-19 subjects treated with Proxalutamide is equal to the distribution of clinical assessments on the COVID-19 ordinal scale at day 14 among hospitalized COVID-19 subjects treated with the Proxalutamide placebo

The Alternative Hypothesis (H_A) is that the distribution of clinical assessments on the COVID-19 ordinal scale at day 14 among hospitalized COVID-19 subjects treated with Proxalutamide is not equal to the distribution of clinical assessments on the COVID-19 ordinal scale at day 14 among hospitalized COVID-19 subjects treated with the Proxalutamide placebo

Mathematically written as:

$$H_0: P(X > Y) = P(Y > X)$$

$$H_A: P(X > Y) \neq P(Y > X)$$

Where X and Y are randomly selected clinical assessments from the two treatment arms in the study.

III. Primary Efficacy Analysis:

- The non-parametric Wilcoxon rank sum test (Mann Whitney U) will be used to assess the primary end point.
- P-values <0.05 will be considered significant. All statistical analysis will be based on the intent-to-treat (ITT) population. All missing data will be described.

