--	--	-------------------------------------------------------------------------------------------------------------------------------------------------------------------------------------------------------------------------------------------------------------------------------------------------------------------------------------------------------------------------------------------------------------------------------------------------------------------------------------------------------------------------------------------------------------------------------------------------------------------------------------------------------------------------------------------------------------------------------------------------------------------------------------------------------------------------------------------------------------------------------------------------------------------------

3. General principles

As proposed in the final protocol	Done in the final statistical Plan	Rationale
Continuous variables will be expressed as median (interquartile range [IQR]) and categorical variables will be expressed as a number	Continuous variables were expressed as median (IQR) and categorical variables were expressed as a number and in a risk percentage.	Expression of the categorical variables only as a number is not sufficient to allow for calculation of risk ratios. Then, absolute risk ratios were calculated for primary (14-day Overall Recovery rate) and secondary outcomes (28-day recovery rate and 28-day all-cause mortality)
95% confidence intervals will be calculated for the primary outcome	95% confidence intervals will be calculated for the primary outcome, secondary outcomes and subgroup analysis.	All secondary outcomes expressed in ratios were reported along with the 95% confidence interval to allow for a better understanding of the effect sizes.
Group comparisons will be analyzed by the Wilcoxon rank sum test or χ^2 test	For all categorial effect sizes, hypothesis testing was performed with the χ^2 test, including risk ratios. 95% Confidence intervals were reported in results tables, for the primary endpoint Overall Recovery Ratio), along with the P value. For the Adverse AE table, P-values were included. Other outcomes described as median and IQR were compared with the Wilcoxon rank sum test.	The primary hypothesis testing previously stated was maintained. However, we explained in which cases the different tests were applied to increase transparency.

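### The Day-14 primary test ignores the Day-1 ordinal score although entry spans scores 3 to 6: a possible loss of precision, not a bias

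*Combined protocol and SAP*

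**What the plan says.** Amended protocol:

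- Section 4.1, criterion 4 admits "Clinical status on the COVID-19 Ordinal Scale (defined in Section 5.1) of 3 to 6". The first protocol version stopped at score 5.
- Section 5.1 defines score 3 as "Hospitalized, not requiring supplemental oxygen - no longer requires ongoing medical care" and score 6 as "Hospitalized, on non-invasive ventilation or high flow oxygen devices".
- Section 5.2 takes the Day-1 score at enrolment, so every subject has one before treatment can act.
- Section 3.3 randomises 1:1 within each sex cohort: "The randomization method used will be permuted blocks of size 4". Baseline score is not a stratum.
- Section 7.1 states: "The primary outcome will be analyzed using the Wilcoxon rank sum test". For rates of clinical improvement it names "unadjusted ordinal logistic regression or Cox proportional hazard models".

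Final statistical plan:

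- Sections 1, 4 and 5 make the primary measure the Day-14 recovery ratio, with recovery meaning score 1 or 2, and align the hypotheses with a chi-square test.
- Section 3 opens its rule with "For all categorial effect sizes, hypothesis testing was performed with the" and names the chi-square test. No stratum or covariate is given.
- Section 2 adds subgroups by baseline score, sex and site without hypothesis tests, and mentions an interaction check of score 6 against 5, 4 and 3. Section 3 adds confidence intervals for the subgroups.
- Section 6 says the sample size still gave 90% power once score 6 was admitted. No calculation is shown.

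**The concern.** The primary measure is being out of hospital by Day 14. On the 8-point scale a subject entering at score 3 is one step from that outcome, and a subject entering at score 6 is four steps away. Baseline score is therefore probably prognostic, though the documents give no recovery rate by score.

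Permuted blocks within sex balance the arm totals, not severity. If one arm happens to receive more score-6 subjects, the unadjusted difference in that trial moves with them. A stratified analysis would remove most of this variation. What is at stake is the precision of the 14-day and 28-day results, and how easily a reader can set aside a baseline imbalance as an explanation for them.

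**Working it through.** **1. The plan's own figure.** Section 7.2 gives N = 12(z_α/2 + z_β)² / [λ²(1 − Σp³)]. With z values 1.960 and 1.282 and λ = ln 2, this is 262.4 / (1 − Σp³), using unrounded quantiles. The stated 294 per cohort follows if Σp³ is about 0.075 with the 3.5% dropout included (294 × 0.965 = 283.7; 1 − 262.4/283.7 = 0.075), or about 0.107 without it (1 − 262.4/294). So 294 is plausible but cannot be confirmed, because the category probabilities are in an external scenario. No term in the formula uses baseline score.

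**2. Assumed inputs.** Mix of scores 3/4/5/6: 5/20/50/25%. Placebo recovery at Day 14 by score:

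- weak gradient: 50/45/40/30%
- moderate: 75/55/40/20%
- strong: 90/70/40/10%

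The overall rates are 39.0%, 39.75% and 41.0%, close to the 39% behind Section 7.2. The effect is a common odds ratio across scores, set so that the overall gain is the 14 points named in final plan section 6.

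**3. Chance imbalance.** The SD of the between-arm difference in the share at score 6, with 300 per arm, is √(2 × 0.25 × 0.75 / 300) = 3.5 points. The SD of the recovery difference due to baseline mix alone is √(2V/n), where V = Σwp² − (Σwp)².

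| Gradient | V | SD, 300 per arm | 95% limit, 300 | 95% limit, 147 |
|---|---|---|---|---|
| Weak | 0.1555 − 0.1521 = 0.0034 | 0.5 points | 0.9 | 1.3 |
| Moderate | 0.1786 − 0.1580 = 0.0206 | 1.2 | 2.3 | 3.3 |
| Strong | 0.2210 − 0.1681 = 0.0529 | 1.9 | 3.7 | 5.3 |

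The limits are 1.96 × SD. With other assumed mixes (5/15/50/30, 2/8/40/50 and 25/25/25/25%) and gradients, the SD at 147 per arm ran from 0.8 to 3.5 points. The chance of exceeding 5 points ran from about 0% to 16%; of exceeding 10 points, at most 0.5%.

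**4. This variation is already in the standard error.** At 300 per arm, with 40% against 54%, the unadjusted SE is √[(0.40 × 0.60 + 0.54 × 0.46)/300] = 4.0 points. The variances in step 3 (2V/300) are about 1%, 8% and 22% of its square. They are counted, not added on top.

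**5. Power, binary recovery.** 20,000 simulated trials per cell; Pearson chi-square against a Cochran-Mantel-Haenszel (CMH) test stratified by Day-1 score, both without continuity correction:

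| Gradient | 147 per arm: unadjusted → stratified | 300 per arm |
|---|---|---|
| Weak | about 69% → 68% | about 94% → 94% |
| Moderate | about 69% → 71% | about 94% → 95% |
| Strong | about 69% → 78% | about 94% → 97–98% |

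**6. Power, 8-point score.** At 142 evaluable per arm (147 × 0.965), mix 5/15/50/30% and odds ratio 2 within each score, power goes from 0.89 (Wilcoxon) to 0.90 (van Elteren) if each baseline point shifts the log-odds by 0.5; from 0.83 to 0.89 if by 1.0; and from 0.73 to 0.86 if by 1.5. If odds ratio 2 is instead meant as the marginal effect, unadjusted power is as planned and stratifying only adds to it.

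**7. Type I error.** With no treatment effect, the unadjusted tests rejected in 4.6% to 5.7% of simulated trials, which is nominal within simulation error.

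**The case against.** The strongest reply is that an unadjusted comparison of randomised arms is valid. Chance imbalance has expectation zero and its variance is inside the reported standard error. That stands in full. A reader might infer that the treatment effect is contaminated by where each arm started, or that false positives are inflated; steps 4 and 7 contradict both. Nor does the protocol define its aim as change from entry. The stated purpose is efficacy in hospitalised patients, the endpoint is status at Day 14, and mean change on the scale is no longer among the outcomes.

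It is also fair that every figure of size rests on an assumed mix and gradient, that the notable gains come from the strong gradient, and that a weak gradient costs about one point. No figure has been worked out for mortality. The 69% starting power at 147 per arm is a separate sample-size matter, not a result of leaving out the covariate.

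The final plan does more with baseline score than nothing: subgroup estimates with intervals and an interaction check. These ask whether the effect varies by severity; they do not adjust the overall estimate. The statement that power was rechecked does not touch the choice of test.

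Finally, the final plan was written alongside the manuscript, so a new primary analysis is one more late choice. That limits how it may be presented, but is no reason to leave it out.

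**Conclusion.** The point holds as one about efficiency. A probably prognostic variable, measured on everyone at entry, is left out of the primary test. Under the assumptions shown, the gain from using it on the binary endpoint at 147 per arm lies between about −1 and +9 percentage points of power, and at 300 per arm between 0 and about +4. Where baseline score predicts little, the gain is close to nil.

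Two stronger readings should be resisted. First, the breadth of the inclusion criterion is not itself an error, and nothing here calls for changing it. Second, final plan section 2 says the randomisation scheme was changed at a small remote hospital. A reader might infer that severity was therefore unbalanced systematically. The documents report no baseline distribution by arm and refer to a supplement that is not included, so this cannot be concluded. The statement that there is no bias does, however, assume sound randomisation, and stratifying by Day-1 score would not repair an allocation fault.

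**What to change.** Change Section 7.1 and final plan sections 3 to 5, not Section 4.1. Replace the unadjusted primary test with one stratified by Day-1 score and by sex cohort, since sex is the randomisation cohort:

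- 8-point score: van Elteren (stratified Wilcoxon) test.
- 14-day recovery, 28-day recovery and 28-day mortality: CMH test without continuity correction, with a Mantel-Haenszel risk ratio and 95% interval.
- Strata: merge score 3 with score 4 where sparse. At the assumed 5%, score 3 would hold about 7 subjects per arm per cohort (147 × 0.05); merged with score 4, about 37 (147 × 0.25).

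Report the unadjusted result beside each. Date the adjusted analysis and label it as added during manuscript preparation, so that it is not read as prespecified.

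The cost is a change of wording and slightly more analysis work on data already collected, with no new subjects or visits. The downside is up to about one point of power if baseline score is only weakly prognostic.
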